6.7 BASELINE, TIME WINDOWS AND CALCULATED VISITS

As a general rule, last assessment before first trial drug intake (included) will be used as baseline. If the baseline value is missing and the screening value is available, then the baseline value will be defined as the screening value taken closest to baseline date.

A windowing will be performed as described in Tables 6.7: 1, 6.7: 2, 6.7: 3 and 6.7: 4, in order to assign data to the relevant study visit based on the actual day of the assessment. Data will be analysed using the re-calculated visits in the statistical tables. However, in the listings, all visits performed will be displayed (even if outside time-window), along with the re-calculated visit.

Table 6.7: 1 Time windowing rules for physical examination, vital signs - Group 1

Time window of actual day ^[1]			Allocated to		
Start day	End day (included)	Length of the time-window [days]	Visit number	Visit name	Planned day of the visit
1	1	1	1, or 2 ^[2]	Baseline	1
2	29	28	3	3 weeks	23
30	Last treatment intake + 27 ^[3]	variable	NA	Between 3 weeks - FU	NA
Last treatment intake + 28	Last treatment intake + 31	4	4	Follow-up	52

[1] First trial drug intake date is taken into account as a reference to calculate time windows

[2] Depending on the last assessment before first trial drug intake (included), refer to Section 6.7 for baseline definition

[3] This period only exists if last treatment intake occurs after 2 days (later than 28 days before 30 days)

Table 6.7: 2 Time windowing rules for physical examination, vital signs - Group 2

Time window of actual day ^[1]			Allocated to		
Start day	End day (included)	Length of the time-window [days]	Visit number	Visit name	Planned day of the visit
1	1	1	1, or 2 ^[2]	Baseline	1
2	12	11	3a	1 week	8
13	19	7	3b	2 weeks	16
20	Last treatment intake + 27 ^[3]	variable	NA	Between 2 weeks - FU	NA
Last treatment intake + 28	Last treatment intake + 31	4	4	Follow-up	44

[1] First trial drug intake date is taken into account as a reference to calculate time windows

[2] Depending on the last assessment before first trial drug intake (included), refer to [Section 6.7](#) for baseline definition

[3] This period only exists if last treatment intake occurs after 6 days (later than 28 days before 20 days)

Table 6.7: 3 Time windowing rules for laboratory measurements – Group 1

Time window of actual day ^[1]			Allocated to		
Start day	End day (included)	Length of the time-window [days]	Visit number	Visit name	Planned day of the visit
1	1	1	1	Baseline	1
2	38	37	3	3 weeks	23
39	No upper limit	NA	4	Follow-up	52

[1] First trial drug intake date is taken into account as a reference to calculate time windows

Table 6.7: 4 Time windowing rules for laboratory measurements – Group 2

Time window of actual day ^[1]			Allocated to		
Start day	End day (included)	Length of the time-window [days]	Visit number	Visit name	Planned day of the visit
1	1	1	1	Baseline	1
2	12	11	3a	1 week	8
13	30	18	3b	2 weeks	16
31	No upper limit	NA	4	Follow-up	44

[1] First trial drug intake date is taken into account as a reference to calculate time windows

If after windowing of visits at baseline, two values fall within the same baseline interval, then the last value will be taken into account. If after windowing of post-baseline visits, two visits fall in the same interval, then the measurement closest to the planned visit will be taken into account. In case two measurements are equidistant from the planned visit, then the last one will be picked. The same rules will be applied for laboratory measurements.

For physical examination and vital signs only, if after windowing of post-baseline visits, two values fall within the same interval “Follow-up” then only the first value will be taken into account.

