	possibility to reduce to two capsules tid (534 mg tid / 1602 mg daily) Day 16 three capsules in the morning only (801 mg, this is the last dose		

Boehringer Ingelheim BI Trial No.: 1199.229 c03463451-08

Trial Protocol Version 4.0

Page 5 of 118 Proprietary confidential information © 2016 Boehringer Ingelheim International GmbH or one or more of its affiliated companies

h			
Name of company:			
Boehringer Ingelheim	1		
Name of finished product:	:		
Ofev®			
Name of active ingredient	:		
Nintedanib			
Protocol date:	Trial number:		Revision date:
17 July 2015	1199.229		29 July 2016
	in the PK period)		
Mode of administration:	Ande of administration: Oral administration with food		
Duration of treatment:	16 days		
Endpoints	Pharmacokinetic Parameters:		
	Group 1:		
	Primary endpoints: AUC _{0-tz} and C _{max} of nintedanib		
	Secondary endpoin	ts: $AUC_{0-\infty}$ of nintedanib	
	Group 2:		
	Primary endpoints.	AUC and Cmar as of nirfenid	one
	1 mary enupoints. $100_{\tau,ss}$ and $C_{max,ss}$ of phreindone		
Safety criteria:	Incidence and intensity of adverse events, physical examination, vital		
	signs, ECG, change from baseline in laboratory parameters		
Statistical methods:	Descriptive statistics and analysis of variance (ANOVA) for AUC _{0-tz} ,		
	C_{max} and AUC _{0-∞} of nintedanib with and without the association with		
	pirfenidone (group	1) and for AUC _{τ,ss} and C _{max,ss} if	for pirfenidone with
	and without the ass	ociation with nintedanib (grou	p 2).

Page 6 of 118

63451-08Trial Protocol Version 4.0Page 6 ofProprietary confidential information © 2016 Boehringer Ingelheim International GmbH or one or more of its affiliated companies

FLOW CHART - GROUP 1

Trial Periods	Screening Period ¹	PK e	valuation	n Period ¹⁰	PK Follow-up Period ¹⁸
Visit	1	2	Phone call ⁶	3 ¹³	4
Weeks		0	2	311	7
Days	-28 to -1	1-2	15	23-24	52
Time window for visits			+	6 days	+3 days
Informed consent ²	Х				
Demographics	Х				
Medical history	Х				
Review of in-/exclusion criteria	Х	Х			
Drug and alcohol testing at site	Х	Х			
Physical examination	Х	Х		Х	Х
Vital signs ³	Х	Х		Х	Х
Laboratory tests	X			Х	Х
Pregnancy test (urine) ⁹	Х	Х		Х	Х
PK sample ⁷		X^{17}		X^{17}	
		Х			
		X ¹⁴		X^{14}	Х
		X^{14}		X^{14}	
12 lead-Electrocardiogram (ECG)	X				Х
Spirometry ¹²	X	Х		Х	Х
DLCO ¹⁹	X	$(X)^{19}$			
Register screening / start of treatment	X	Х			
Dispense trial drugs ⁴		X ¹⁷		Х	
Collect trial drug & compliance check				Х	
Dispense and/or collect & review diary ⁵		X^{17}		Х	

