AEs and Concomitant therapy ¹⁶	X	X ¹⁷	X	X ¹⁷	Х
Conclusion of PK evaluation period				Х	
Conclusion of subject participation					X ¹⁵

FOOTNOTES – GROUP 1

- 1. The screening period between Visit 1 and 2 should last a maximum of 28 days. Eligible patients can be started on treatment once central lab results have been received and are found to be consistent with eligibility criteria.
- 2. At site discretion, informed consent may be obtained on one day and the remainder of the screening procedures can follow.
- 3. Vital signs to include blood pressure and pulse rate.
- 4. Patient will be dispensed three wallets of pirfenidone. They will use one wallet to uptitrate for 14 days (Day 2 to Day 15) and then the next wallet for the complete dose of 801 mg tid daily (Day 16 to Day 22). On Day 23 the patient should bring their medication into clinic and will be given the morning and the 14:00 of pirfenidone at the clinic. They will take their evening dose at home and this will be their final dose during the PK period. The patient will also be dispensed a single 150mg dose of nintedanib on Day 1 and Day 23. (See Section 4.1.4).
- 5. Patients will be supplied with a diary and a dosing card and they will be asked to document the number of capsules they have taken each day and also to record any adverse events during this period.
- 6. At the end of the 14 day uptitration (Day 15) a call will be made to the patient to check whether there have been any issues with uptitration and when the patient has reached the full dose (the phone call should be documented in the patient notes). The patient will then continue on full dose (801 mg tid) for 7 consecutive days (Day 16 to Day 22) before returning to the clinic for the next PK day (Day 23). The patient would have their final PK sample taken on Day 24.
- 7. Please see separate PK flowchart Group 1 for details during the PK evaluation period Section 10.2.
- 8.
- 9. Urine dipstick pregnancy tests will be provided by central lab and should be performed in all women of childbearing potential.
- 10. If a patient withdraws from the PK evaluation period or does not tolerate uptitration then the patient should be managed according to Figure 4.1.4:1
- 11. The patient will stop all trial medication on Day 23 and have a washout period from study drug until the PK FU visit.
- 12. Spirometry should be conducted using local standard equipment.

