- Remind patient not to take morning dose of study medication on the day of Visit 3 and to bring their study medication with them to the clinic and also the diary card.

Visit 3 Day 23

Once the patient has been on stable, full dose pirfenidone for 7 days (a 6 day window is allowed to ensure 7 consecutive days) they will return to clinic for the next PK day.

The patient should attend the clinic at approximately 07:00 so that the following assessments can be started before breakfast is given:

- Physical examination and vital signs.
- Urine pregnancy test for women of childbearing potential.
- Blood sample for laboratory tests (Section 5.3.3)
- Pre-dose PK samples should be taken according to PK Flowchart (Group 1, this should be taken prior to the other blood samples).
- •
- Spirometry.
- Review concomitant therapy and any adverse events since previous visit and throughout the day at regular intervals.
- Patients will return all unused medication. Medication compliance will be assessed by counting returned (unused) capsules.
- The patient will return the diary card and this will be reviewed to check that the patient has received seven consecutive, stable days of treatment.
- One 150mg nintedanib capsule and three 267 mg pirfenidone capsules should be given to the patient at should be given to the patient at 08:00 during breakfast (See PK Flowchart – Group 1).
- PK samples should be taken according to PK Flowchart (Group 1).
- The patient should be given lunch at 12:00.
- Three 267 mg pirfenidone capsules will be given to the patient at 14:00 along with a snack.
- A snack will also be given to the patient at 16:00.
- After the PK time point at 18:00, the patient can leave the clinic.
- The patient should take the final dose of three 267 mg pirfenidone capsules at home at approximately 20:00 with food and a glass of water.

Visit 3 Day 24

- The patient must return the next morning (Visit 3 Day 24) for the 24 hour PK time point at 07:55 the next day.
- AEs and concomitant medications should also be assessed.
- Other assessments listed for Visit 3 in the PK Flowchart are conducted at Day 23
- No study drugs are given.
- Remind patient of PK FU visit scheduled for 28 days after this visit.

PK Follow-up/ End of Trial

The patient should return to the clinic 28 days or more after Visit 3 Day 24 for their PK Followup/ End of Trial Visit as detailed in section 6.2.3.

Group 2

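### SAP Table 6.7:1 closes the Group 1 vital-signs Follow-up window at last intake + 31 (Day 54), but the protocol allows Visit 4 on Day 55

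*SAP*

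**What the plan says.** **SAP.** Section 6.7 re-assigns assessments to visits by actual study day, counted from first drug intake, and the tables use the result: "Data will be analysed using the re-calculated visits in the statistical tables". Listings still show every visit, inside a window or not. For physical examination and vital signs, the last row of Table 6.7:1 (Group 1) and of Table 6.7:2 (Group 2) is Follow-up. It starts at last intake + 28 and ends at "Last treatment intake + 31", a length of 4 days. The planned days are 52 and 44. For laboratory data, the Follow-up rows of Tables 6.7:3 and 6.7:4 end with "No upper limit". If two vital-signs values fall in Follow-up, "then only the first value will be taken into account". Section 7.8.3 plans descriptive vital-signs summaries by visit and as change from baseline.

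**Protocol.** In Group 1 the last dose is on the evening of Day 23 (flow chart, footnote 4): "They will take their evening dose at home and this will be their final dose during the PK period". The flow chart places Visit 4 on Day 52, and its row "Time window for visits" gives + 3 days. Section 6.2.2, under Visit 3 Day 24, says: "Remind patient of PK FU visit scheduled for 28 days after this visit". The same section sets the follow-up visit at 28 days or more after Day 24. Footnote 18 of the Group 1 flow chart counts at least 28 days from last intake, and section 6.2.3 counts at least 28 days from the end of treatment.

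**The concern.** In Group 1 the last PK day (Day 24) is one day after the last dose (Day 23). The SAP counts from the last dose; the flow chart and section 6.2.2 count from Day 24. A window as long as the protocol's tolerance but counted from a day earlier misses the last permitted day.

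A vital-signs value from that day has no row in Table 6.7:1, so on a plain reading it is listed but not summarised. The laboratory sample from the same visit is summarised. The Follow-up line of one safety table would then omit a patient who kept to the schedule, while the Follow-up line of another includes that patient.

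**Working it through.** **The SAP's own figures.** Follow-up length is 31 − 28 + 1 = 4 days, as stated. Footnote 3 of Table 6.7:1 reads "This period only exists if last treatment intake occurs after 2 days", and 30 − 28 = 2 agrees. So last intake + k is plain addition of study days.

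**Group 1 completer, last intake on Day 23**
- SAP window: 23 + 28 = 51 to 23 + 31 = 54.
- Flow chart and section 6.2.2: 24 + 28 = 52, then 52 + 3 = 55.
- Footnote 18 with the same 3-day tolerance: 23 + 28 = 51, then 51 + 3 = 54.
- Day 55 is 55 − 23 = last intake + 32. It is inside the flow-chart window and in no SAP row.
- Laboratory Follow-up starts on Day 39 and is open-ended, so a Day 55 sample is tabulated.

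The SAP window matches footnote 18 plus 3 days. The protocol's two reference days differ by one day, and the SAP covers one of them.

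**Group 2 completer, last intake on Day 16.** SAP window: 16 + 28 = 44 to 16 + 31 = 47. Flow chart: 44 to 44 + 3 = 47. Nothing is lost.

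**Visit 3 delayed by s = 1 to 6 days (Group 1).** Last intake is 23 + s and the SAP window ends on Day 54 + s. If Visit 4 moves with Visit 3, its last permitted day is 55 + s (Days 56 to 61), and that one day is again lost. If Visit 4 stays on Days 52 to 55, Day 55 is last intake + 32 − s, which is + 31 down to + 26, so nothing lies past the end. Section 6.1 does not clearly settle which applies.

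**Patients who stop drug before Visit 3 or 3b.** Protocol section 4.1.4 has patients who do not reach seven stable days stop medication and still attend Visit 3 or 3b, and section 6.2.2 counts Visit 4 from that visit. Assume that they keep the flow-chart days. A permitted day is lost when it exceeds last intake + 31:

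| Group | Last intake | SAP window ends | Permitted days lost |
|---|---|---|---|
| 1 (Days 52–55) | 23 | 54 | 55 |
| 1 | 22 | 53 | 54–55 |
| 1 | 21 | 52 | 53–55 |
| 1 | 20 | 51 | 52–55 (+ 32 to + 35) |
| 2 (Days 44–47) | 16 | 47 | none |
| 2 | 15 | 46 | 47 (+ 32) |
| 2 | 12 | 43 | 44–47 |

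**Candidate fixes.** Ending the window at + 32 closes the gap for Group 1 completers (23 + 32 = 55) but not for last intake on Day 20, where Days 53 to 55 (+ 33 to + 35) stay out. With no upper limit, every visit from last intake + 28 onward is assigned in both groups.

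**The case against.** The strongest reply is that the SAP follows the protocol. Footnote 18 is attached to the follow-up period in the flow chart and counts from last intake, section 6.2.3 counts from the end of treatment, and planned Day 52 lies inside the SAP window. This stands in part: the mismatch begins in the protocol, which has two reference days. But footnote 18 and section 6.2.3 set only a minimum. Neither makes Day 55 late, and the flow chart expressly permits it.

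The second reply is that the matter is trivial. Every visit stays in the listings, clinically relevant vital-sign changes are recorded as adverse events (Protocol section 5.3.8), and physical examination findings are not tabulated separately (SAP section 7.8.5). This stands, and it sets the rating.

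A third reply is that an upper limit keeps very late values out of the Follow-up summary. That is a fair purpose, but the SAP does not apply it to laboratory data from the same visit.

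A reader might also infer that follow-up laboratory samples of early stoppers are misfiled under the 3-week visit in Table 6.7:3. The documents do not establish this. It depends on how follow-up is timed in Figure 4.1.4:1, which cannot be read here, and when two values share a window the one nearest the planned day is used.

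**Conclusion.** Wrong as written, minor. For a Group 1 patient with last intake on Day 23, one of the four flow-chart days for Visit 4 (Day 55, last intake + 32) falls outside every window, and its vital signs are left out of the by-visit table. This rests on the stated dosing and visit days and on reading an unassigned value as not tabulated.

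Two extensions are conditional. With a delayed Visit 3, the same one-day loss recurs only if Visit 4 moves too. For early stoppers, the loss grows to as many as four permitted days and reaches Group 2 only if they keep the flow-chart visit days. It would therefore be wrong to treat the gap as always one day, or Group 2 as always free of it.

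A reader might go further and infer biased safety results or a known number of lost patients. The documents support neither. They do not say how many visits will fall on the affected days, and no direction of bias follows. Listings, adverse events, liver maxima and PK endpoints are unaffected.

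**What to change.** In SAP Tables 6.7:1 and 6.7:2, replace the end of the Follow-up row with "No upper limit" and its length with NA, as in Tables 6.7:3 and 6.7:4. The existing first-value rule for Follow-up already handles duplicates.

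The protocol's two reference days for Visit 4 (last intake or end of treatment, and Day 24) should also be reconciled, or the SAP should note that they differ.

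The cost is two table rows and the matching programming before database lock, with no new data. The downside is that an occasional late, off-schedule value will be tabulated as Follow-up; the listings show its actual timing.

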- 13. The uptitration phase between Visit 2 and Visit 3 can be extended by a maximum of 6 days if the patient needs longer to uptitrate or to achieve 7 consecutive stable days at full dose.
- 14.
- 15. At Visit 4 (PK FU) the optional nintedanib Named Patient Programme will be discussed with the patient.
- 16. AEs and concomitant therapy should be checked at regular intervals during the PK days.
- 17. At Visit 2 Day 2 and Visit 3 Day 24 only these procedures need to be done see Section 6.2.2.
- 18. The PK Follow Up visit should occur at least 28 days after last drug intake.
- 19. DLCO testing will be performed once at visit 1 or 2, or during the screening period (visit 1 to visit 2). The results will be corrected for haemoglobin by the site, see section 10.3 for further details.

Page 8 of 118

Proprietary confidential information © 2016 Boehringer Ingelheim International GmbH or one or more of its affiliated companies

FLOW CHART - GROUP 2

Trial Periods	Screening Period ¹	PK ev	aluation pe	eriod ⁹	PK Follow- up Period ¹⁶
Visit	1	2	3 a	3b ¹²	4
Weeks		0	1	2	6
Days	-28 to -1	1	8	16 ¹⁰	44
Time window for visits			+3 days	+3 days	+3 days
Informed consent ²	Х				
Demographics	Х				
Medical history	Х				
Review of in-/exclusion criteria	Х	Х			
Drug and alcohol testing at site	Х	Х			
Physical examination	Х	Х	Х	Х	Х
Vital signs ³	Х	Х	Х	Х	Х
Laboratory tests	Х		Х	Х	Х
Pregnancy test (urine) ⁸	Х	Х	Х	Х	Х
PK sample ⁶			Х	Х	
		Х			
		Х	X ¹³	X ¹³	Х
		Х	X ¹³	X ¹³	
	Х				Х
Spirometry ¹¹	Х	Х	Х	Х	Х
DLCO ¹⁷	Х	$(X)^{17}$			
Register screening / start of treatment	Х	Х			
Dispense trial drugs ⁴		Х	Х	Х	
Collect trial drug & compliance check			Х	Х	
Dispense and/or collect & review diary ⁵		Х	Х		
AEs and Concomitant medication ¹⁵	Х	Х	Х	Х	Х
Conclusion of PK evaluation period				Х	
Conclusion of subject participation					X ¹⁴

FOOTNOTES – GROUP 2

- 1. The screening period between Visit 1 and 2 should last a maximum of 28 days. Eligible patients can be started on treatment once central lab results have been received and are found to be consistent with eligibility criteria.
- 2. At site discretion, informed consent may be obtained on one day and the remainder of the screening procedures can follow.
- 3. Vital signs to include blood pressure, pulse rate and weight.

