6. INVESTIGATIONAL PLAN

6.1 **VISIT SCHEDULE**

Informed consent of all study patients will be obtained in compliance with ICH and GCP guidelines and the principles stipulated in the Declaration of Helsinki prior to any study related procedures, including washout of restricted medications.

The study will consist of three sequential periods; a screening period, a PK evaluation period, and the follow-up period.

Screening will be up to 4 weeks (28 days) in duration. The PK evaluation period will be 24 days in Group 1 and 16 days in Group 2 plus a follow up period of 28 days.

All patients are to adhere to the visit schedule as outlined in flowchart 1 and flowchart 2. Some flexibility is allowed in scheduling the visits according to the visit time windows specified. The trial medication dispensed allows for these time windows. All deviations from the planned schedule will be documented. If any visit is to be rescheduled, subsequent visits should follow the previous visit date schedule. No protocol waivers will be given (e.g. sponsor will not grant permission to include a known ineligible patient).

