10.2 TIME SCHEDULE FOR PHARMACOKINETIC (PK) BLOOD SAMPLING

GRO	UP 1 – 1	PK tin	ne points				
Visit	Day	Window	Planned Time [h:min]	Approximate clock time of actual day [h:min]	Event and comment	PK ^{blood} for nintedanib	PK _{blood} for pirfenidone
2	1		-1:00	7:00	Predose ¹	Х	Х
			0:00	8:00	Breakfast ^{2,} Drug administration nintedanib ³		
			0:30	8:30		Х	
			1:00	9:00		Х	
			2:00	10:00	Glass of water	Х	
			3:00	11:00		Х	
			4:00	12:00	Glass of water, Lunch	Х	
			6:00	14:00		Х	
			8:00	16:00	Snack	Х	
			10:00	18:00		Х	
	2		23:55	7:55		Х	
			24:00	8:00	Snack, Drug administration of pirfenidone and begin uptitration ⁶		
3	23	+6	527:00	7:00	Predose	Х	Х
			528:00	8:00	Breakfast ^{2,} Drug administration nintedanib and pirfenidone		
			528:30	8:30		Х	Χ
			529:00	9:00		Х	Χ
			530:00	10:00	Glass of water	Х	Х
			531:00	11:00		Х	Х
			532:00	12:00	Glass of water, Lunch	Х	X
			534:00	14:00	Snack, Drug administration pirfenidone ^{4,5}	Х	X
			536:00	16:00		Х	Х
			538:00	18:00		X	X
	24		551:55	7:55		Х	X

Footnotes Group 1

- 1. Predose PK sample can be taken prior to breakfast and administration of trial drugs.
- 2. Breakfast should consist of a continental breakfast and drug should be administered with the meal.
- 3. Single 150 mg dose of nintedanib given to the patient at the clinic with a glass of water.
- 4. On PK day 23, it is requested that the patient take their midday pirfenidone dose at 2pm so that there will be a 6 hour profile.
- 5. On Day 23, the evening dose of pirfenidone will be taken at home at approximately 20:00. This will be the last dose of pirfenidone taken.
- 6. The midday and evening doses of pirfenidone will be taken at home.

Page 79 of 118

Proprietary confidential information © 2016 Boehringer Ingelheim International GmbH or one or more of its affiliated companies

GROUP 2 – PK time points

Visit	Day	Window	Planned Time [h:min]	Approximate clock time of actual day [h:min]	Event and comment	PK _{blood} for nintedanib	PK _{blood} for pirfenidone
3a	8	+3	-1:00	7:00	Predose ¹	Х	Х
			0:00	8:00	Breakfast ² , Drug administration pirfenidone		
			0:30	8:30			Х
			1:00	9:00			Х
			2:00	10:00	Glass of water		Х
			3:00	11:00			Х
			4:00	12:00	Glass of water, Lunch		Х
			5:55	13:55			Х
			6:00	14:00	Snack, Drug administration pirfenidone ³ and dispense nintedanib ⁵		
3b	16	+3	191:00	7:00		Х	Х
			192:00	8:00	Breakfast, Drug administration nintedanib and pirfenidone ⁴		
			192:30	8:30		Х	Х
			193:00	9:00		Х	Х

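### SAP Table 6.7:1 closes the Group 1 vital-signs Follow-up window at Day 54, one day before the last day the protocol allows for Visit 4

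*SAP*

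**What the plan says.** **Protocol, Group 1.** The flow chart places Visit 4 on Day 52, and its row "Time window for visits" gives + 3 days for that visit. Dosing ends on Day 23: flow chart footnote 11 says so, and section 10.2, Group 1 footnote 5, says of the evening dose on that day: "This will be the last dose of pirfenidone taken". Two statements set a minimum interval. Flow chart footnote 18: "The PK Follow Up visit should occur at least 28 days after last drug intake". Section 6.2.2: "The patient should return to the clinic 28 days or more after Visit 3 Day 24".

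**SAP 6.7, Table 6.7:1 (physical examination and vital signs, Group 1).** The table prints Day 52 as the planned day of Follow-up. The window runs from last intake + 28 to "Last treatment intake + 31", with a stated length of 4 days, and it is the last row. The same upper limit stands in Table 6.7:2 for Group 2, where it is correct. On use, the SAP says: "Data will be analysed using the re-calculated visits in the statistical tables". Listings show every visit, including those outside a window.

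**SAP 6.7, Table 6.7:3 (labs, Group 1).** Days are counted from first intake only. Day 2 to Day 38 is the 3-week visit. Day 39 onward is Follow-up, with no upper limit.

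**The concern.** A windowing table should give every protocol-compliant visit a place. Here the protocol counts Visit 4 from the second PK day (Day 24), while the SAP counts from the last dose (Day 23) and keeps a 4-day width. The SAP window therefore sits one day earlier than the protocol window. It takes in Day 51, which is before the planned day, and omits Day 55, which is allowed.

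SAP 7.8.3 reports vital signs by visit and as change from baseline, using the re-calculated visits. A compliant Day 55 value would be missing from the Follow-up row with no protocol deviation to explain it. Labs drawn at that same visit would be counted as Follow-up, because the lab window is open-ended.

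**Working it through.** **Inputs**
- Last intake: Group 1 Day 23 (protocol flow chart footnote 11; section 10.2); Group 2 Day 16 (Group 2 flow chart footnote 10).
- Visit 4: Group 1 Day 52 + 3; Group 2 Day 44 + 3 (flow charts).
- SAP Follow-up window: last intake + 28 to + 31, inclusive (Tables 6.7:1 and 6.7:2).

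**Reproducing the plan's figures**
- Window length: 31 − 28 + 1 = 4 days, as printed.
- Group 1 planned day: 24 + 28 = 52, as printed.
- Group 2: 16 + 28 = 44 and 16 + 31 = 47. This equals the protocol window of Day 44 to 47 and confirms the counting convention.

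**Group 1, Visit 3 on schedule**

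| | First day | Last day | Relative to last intake |
|---|---|---|---|
| Protocol Visit 4 | 52 | 52 + 3 = 55 | + 29 to + 32 |
| SAP Follow-up | 23 + 28 = 51 | 23 + 31 = 54 | + 28 to + 31 |

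Day 55 is 55 − 23 = 32 days after last intake. It lies beyond the last row, so 1 of the 4 permitted days has no visit.

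**Group 1, Visit 3 delayed by s days (s = 1 to 6).** The SAP window becomes Day 51 + s to 54 + s. Protocol 6.1 says of a rescheduled visit that "subsequent visits should follow the previous visit date schedule", which can be read two ways.
- If Visit 4 moves with Visit 3, it is allowed on Day 52 + s to 55 + s, and the last day is always outside. Example, s = 6: protocol Day 58 to 61, SAP Day 57 to 60.
- If Visit 4 stays at Day 52 to 55, no permitted day is outside. This reading cannot hold for long delays: footnote 18 requires Day 51 + s or later, which is beyond Day 55 for s = 5 or 6. Section 6.2.2 requires Day 52 + s or later, which is beyond Day 55 for s = 4 to 6.

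The point does not depend on this choice, because the on-schedule case already shows the gap.

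**Optional note, labs in Group 1.** Let L be the day of last intake and L + k the day of Visit 4. The follow-up lab is labelled as the 3-week visit when L + k ≤ 38:

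| k | 28 | 29 | 30 | 31 | 32 |
|---|---|---|---|---|---|
| L at most | 10 | 9 | 8 | 7 | 6 |

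In Group 2 the lab Follow-up row starts on Day 31, so at k = 28 the condition is L ≤ 30 − 28 = 2. This is in effect a Group 1 matter.

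**The case against.** The best defence is that the SAP follows protocol text that counts from last intake. Footnote 18 and section 6.2.3 both ask for at least 28 days after treatment, and + 28 with a 3-day tolerance gives + 28 to + 31. That explains the rule but does not remove the gap. Both statements set only a minimum, and neither shortens the explicit Day 52 + 3 window. Section 6.2.2 and the SAP's own planned day also point to Day 52.

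On weight, the defence is sound. Sites are told to book Visit 4 for 28 days after Day 24, which is Day 52 and inside the SAP window. Only the last tolerance day is lost. A reader might infer from 1 of 4 days that a quarter of follow-up values are at risk. The documents give no distribution of visit days, so that does not follow. A reader might also infer that safety data are lost. They are not: listings show every visit, and clinically relevant vital-sign changes are recorded as adverse events (protocol 5.3.8).

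For labs, a reader might infer that Table 6.7:3 is wrong, or that a follow-up sample will displace the Visit 3 sample. The documents support neither.
- Counting from first dose with a cut near the midpoint of the planned days, (23 + 52) / 2 = 37.5, is a defensible convention.
- SAP 6.1 treats data up to 28 days after last intake as on-treatment, so a lab at exactly + 28 is on-treatment by that definition. From + 29 the limit is Day 9.
- Displacement depends on when an early stopper attends Visit 3. The text does not fix that, and Figure 4.1.4:1 is not shown. A Visit 3 near Day 23 keeps its own lab.

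What remains is a difference in labelling. Footnote 3 of Table 6.7:1 ("This period only exists if last treatment intake occurs after 2 days") shows that early stops were considered for vital signs. The lab table has no matching rule, so vital signs and labs from one visit can carry different labels.

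**Conclusion.** The vital-signs point stands with high confidence as a minor error in a stated rule. For a Group 1 completer with an on-schedule Visit 3, Day 55 is permitted by the protocol and has no row in SAP Table 6.7:1. This rests only on the last dose being on Day 23 and on the flow chart tolerance applying to Visit 4, both of which are explicit.

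The effect is confined to the descriptive by-visit vital-signs tables. With about 16 patients planned for Group 1, one omitted value would be 1/16, or about 6%, of the Follow-up row. How many patients would be affected is not known and may be none. Physical examination shares the table but has no separate by-visit analysis (SAP 7.8.5). AE assignment, worst-value liver tables and PK endpoints do not use this window.

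The lab note is optional and of lower confidence. It needs a Group 1 patient whose last intake is by about Day 10, and it changes a row label in a descriptive table.

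**What to change.** In SAP Table 6.7:1, end the Group 1 Follow-up window at last intake + 32, which makes its length 32 − 28 + 1 = 5 days (Day 51 to 55), or leave it open-ended as in the lab tables. The open-ended form also covers later visits, which the minimum-interval wording does not exclude. Leave Table 6.7:2 as it is; Group 2 needs no correction.

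Optional: in Table 6.7:3, start lab Follow-up at the earlier of Day 39 and last intake + 28, and end the 3-week row the day before. This aligns labs with the vital-signs rule for early stoppers.

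The cost is one table row, one optional rule and the matching programming. No visit, sample or protocol amendment is needed.
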